2. STUDY OBJECTIVES

The objectives of this study are:

1. To demonstrate non-inferiority of BPL HRIG compared to an FDA-licensed HRIG product, in terms of the proportion of subjects achieving anti-rabies antibody titer of ≥ 0.5 IU/mL at Day 14 following treatment with HRIG in conjunction with active rabies vaccine.

2. To compare the PK of BPL HRIG in conjunction with active rabies vaccine, with FDA-licensed HRIG product in conjunction with active rabies vaccine.
3. To assess whether BPL HRIG interferes with the development of the host-immune response when given simultaneously with active rabies vaccine, relative to an FDA-licensed HRIG product.
4. To evaluate the safety and tolerability of BPL HRIG in comparison with FDA-licensed HRIG product.

3. SAMPLE SIZE AND POWER COMPUTATION

Statistical calculations indicate a minimum of ■ subjects per group is necessary. To allow for a ■ rate of subject withdrawal or unevaluable data, approximately 81 subjects will be enrolled per group.

This study is powered based on a ■ test with an overall study α of ■. A total of 162 subjects will be randomized to achieve ■ power with a one-sided significance level of ■. This computation accounts for an expected 10% dropout rate resulting in 146 evaluable subjects. The following table outlines the underlying assumptions.

	Day 14 \geq 0.5 IU/mL
Non-inferiority Margin	■
Difference	■
% Success	98%

4. STUDY DESIGN

This will be a prospective, randomized, double-blind, parallel-group, non-inferiority, phase II/III study of the safety and effectiveness of simulated post-exposure prophylaxis with BPL HRIG with co-administration of active rabies vaccine in healthy subjects. This is intended to be a multi-center study. Treatment assignment is blinded until post database lock.

Subjects will be randomized 1:1 to one of the 2 treatment groups, as follows:

HRIG treatment	Rabies vaccine treatment	# of Subjects
BPL HRIG	active rabies vaccine	81
comparator HRIG	active rabies vaccine	81

Prior to randomizing a participant, all screening and baseline evaluations must be completed and the participant determined to be eligible for inclusion in the study. Randomization and the baseline visit (Day 0) should occur no later than 28 days after the completion of the screening visit.

All medicinal product preparation will be performed by the site pharmacist using aseptic techniques and according to a standardized procedure on Day 0, and administration of HRIGs + vaccine will be administered an unblinded nurse administrator. All study assessments and Post Day 0 treatment administration will be performed by blinded study personnel. Investigators and subjects will be blinded to treatment assignment.

Subjects will be identified by a unique five-digit number as follows: each site will be allocated a two-digit site number (e.g. Site 01, etc) and each subject will be allocated a three-digit subject number (e.g. 001) at the Screening Visit. Each subject will be identified by the unique site and subject number combination (e.g. 01001).

5. SCHEDULE OF ASSESSMENTS

Each subject will undergo a total of 8 visits. Subjects' eligibility will be assessed at Screening, which can occur up to 28 days prior to dosing. Following a repeat eligibility check at Day 0, eligible subjects will be randomized and dosed with the randomized treatment (HRIG/vaccine or Comparator HRIG/vaccine on Day 0. Further administration of rabies vaccine, PK sampling and safety assessments will be conducted on Days 3, 5 (PK sampling only), 7, 14 and 28. An additional visit for PK sampling and safety assessment will take place on Day 49 (7 weeks) and Day 140 (20 weeks). The last visit will be the End-of-Study Assessment which will take place on Day 140 (20 weeks). This visit will comprise the final PK sample and safety assessments. The end of the trial is

defined as the last subject’s last End-of-Study Assessment (or the date of their last data collected, if the subject has an AE at the End-of-Study Assessment that needs to be followed).

Visit Number	1	2			3	4	5	6	7	8	9
Visit Assessment	Screening	Baseline									End-of-Study Assessment
Visit Timing	up to Day -28	Day 0			Day 3	Day 5	Day 7	Day 14	Day 28 (±2 days)	Day 49 (±4 days)	Day 140 (±7 days)
		pre-dose	dosing	30 min post-dose							
Informed Consent ^a	X										
Demography/Medical History	X										
Eligibility	X	X									
Physical Examination	X									X	X
Height	X										
Weight	X	X ^b									X
ECG	X										X
Vital Signs	X	X							X	X	X
Body Temperature (oral)		X			X		X	X	X		
Pregnancy Test ^c	X	X									X
Hematology, Serum Biochemistry, Urinalysis	X										X
Virology: HBsAg, HCV, HIV	X										X
Markers of Hemolysis: Direct Coomb’s Test, LDH, Plasma Free Hemoglobin, Serum Haptoglobin, Serum bilirubin, Urine Hemosiderin		X			X ^{d,k}	X ^{d,k}	X ^{d,k}	X ^{e,k}			
Archive Serum Sample*		X									X
Randomization ^f		X									
Administration of BPL HRIG / Competitor HRIG			X								
Administration of Active Rabies Vaccine			X		X		X	X	X		
Rabies Virus Neutralizing Antibody		X			X ^e	X ^f	X ^e	X ^e	X ^e	X	X
Reserve Sample Collection ^h	X	X			X	X	X	X	X	X	X
Adverse Events	X	X	X	X	X	X	X	X	X	X	X
Injection Site Observations ⁱ		X		X							
Concomitant Medications	X	X			X	X	X	X	X	X	X

^a informed consent prior to screening procedures
^b for re-assessment of eligibility and calculation of volume to be administered
^c females of childbearing potential only: serum at screening and End-of-Study Assessment, urine dipstick pre-dose on Day 0
^d if the Day 3 Direct Coomb’s test is positive or not available by Day 5, all markers will be tested at Day 5. Subsequent testing at Day 7 and Day 14 will only be performed if results at the previous visit are suggestive of hemolysis
^e if hemolysis is indicated at Day 7, all markers will be tested at Day 14
^f after all screening and baseline procedures have been completed and the subject is confirmed as eligible
^g prior to dose of active rabies vaccine

^h 2 samples will be collected at each timepoint, except for the Baseline Visit (Day 0) and the End-of-Study (EOS) Assessment (Day 140) at which 3 samples will be taken.

The additional plasma reserve samples will be taken in case viral nucleic acid testing is required to confirm viral serology results (see Section 8.2.3) to be assessed at each subsequent visit until no symptoms are observed

ⁱ to be assessed at each subsequent visit until no symptoms are observed

^j bloods draw only **NO** vaccine at this visit

*archive serum sample-pre-dose, Day 0 and EOS, to be archive for approximately 15 years

^k routine hematology, chemistry or urinalysis can be repeated if clinically indicated or at the request of the medical monitor

6. STUDY ENDPOINTS

The PRIMARY efficacy endpoint is to demonstrate non-inferiority of BPL HRIG compared to a FDA-licensed HRIG product, in terms of:

- the proportion of subjects with anti-rabies antibody titer of ≥ 0.5 IU/mL on day 14 after administration of BPL HRIG and vaccine versus comparator HRIG and vaccine, using a non-inferiority margin of 10%.

The SECONDARY efficacy endpoints are as follows:

1. Assessment of AUC_{0-7days} for BPL HRIG+vaccine vs. comparator HRIG+vaccine using a non-inferiority margin of 20%.
2. Comparison of the geometric mean titers (GMTs) for anti-rabies antibody titer at Days 3, 5, 7, 14, and 28 after administration of BPL HRIG and vaccine versus comparator HRIG and vaccine.
3. The proportion of subjects reaching anti-rabies antibody titer of ≥ 0.5 IU/mL at Days 3, 5, 7, 14, 28, 49, and 140 after administration of BPL HRIG and vaccine versus comparator HRIG and vaccine.
4. The proportion of subjects reaching anti-rabies antibody titer of \geq the lower limit of quantitation of the assay at Days 3, 5, 7, 14, 28, 49 and 140 after administration of BPL HRIG and vaccine versus comparator HRIG and vaccine.
5. Comparison of the geometric mean titers (GMTs) for anti-rabies antibody titer at Days 14, 28, 49, and 140 after administration of BPL HRIG and vaccine versus comparator HRIG and vaccine to assess the inhibitory effects of BPL HRIG on active immunization relative to that of the comparator HRIG.

An EXPLORATORY efficacy endpoint is as follows:

The following PK parameters for anti-rabies antibody concentrations for both treatment groups:

- C_{\max} [IU/mL]
- T_{\max} [day]
- area under the concentration vs time curve to the last measurable concentration (AUC_{0-t}) [day*IU/mL]
- apparent terminal rate constant (λ_z) [day^{-1}]
- $AUC_{0-7 \text{ days}}$ [day*IU/mL]
- area under the concentration vs time curve to infinity ($AUC_{0-\infty}$), if appropriate
- $C_{\max}/AUC_{0-\infty}$ [or C_{\max}/AUC_{0-t} if $AUC_{0-\infty}$ cannot be estimated]
- half-life ($t_{1/2}$), if appropriate

The following will be used to assess the SAFETY of BPL HRIG and vaccine, versus comparator HRIG and vaccine:

- Adverse events
- Injection site observations
- Viral serology
- Serum biochemistry, hematology and urinalysis
- Markers of hemolysis
- Physical examination
- Vital signs

The following additional tests will additionally be performed:

- pregnancy tests (for females of childbearing potential).

7. GENERAL ANALYSIS CONVENTIONS

All tables, figures and listings will be produced using SAS (v9.4 or a more recent version).

Unless otherwise stated, categorical data will be presented using counts and percentages, whilst continuous variables will be presented using the mean, 95% confidence interval for the mean, standard deviation (SD), median, minimum, maximum, number of subjects (n) and number of missing subjects or data points. Minima and maxima will be quoted to the number of decimal places as recorded in the CRF; means, SDs and medians will be quoted to one further decimal place. Percentages will be rounded to one decimal place.

Subjects who withdraw from the analysis will have their data analyzed to the point of withdrawal. Subjects who complete all required assessments up to and including Day 14 will be eligible for the primary PK population. Other subjects who withdraw from the study will be eligible for the ITT population. Unblinded subjects will continue in study after being unblinded unless noted otherwise.

For the purpose of the statistical analyses visit labels may be used interchangeably as Visit and Day as in the table below regardless of actual timing of study visit. Sensitivity analyses will be performed to address any potential visit timing issues.

Visit Label	Visit 1	Visit 2	Visit 3	Visit 4	Visit 5	Visit 6	Visit 7	Visit 8	Visit 9
Intended Day	Day -28	Baseline, Day 0	Day 3	Day 5	Day 7	Day 14	Day 28	Day 49	Day 140

a. DEFINITION OF STATISTICAL SIGNIFICANCE

- Primary Efficacy Endpoint

The BPL HRIG treatment effect will be considered non-inferior to the active comparator HRIG treatment when the resultant p-value from the one-sided Farrington-Manning

Score Test for proportion difference is [REDACTED].

- Secondary Efficacy Endpoints

The secondary efficacy endpoint analyses will be considered statistically significant using a two-sided significance level of 0.05.

b. ANALYTIC POPULATIONS

The following analysis populations will be defined for this study.

- Intent-to-Treat [ITT] Population

The intent-to-treat (ITT) population will include all randomized subjects. All analyses will be performed using the ITT population.

- Safety Population

The safety population will be defined as all subjects who receive at least one dose of BPL HRIG / comparator HRIG. Safety data will be analyzed up to the point of withdrawal for applicable subjects. The safety population will be used for all safety analyses.

- Per Protocol [PP] Population

The per protocol population will be split into the **primary** and **secondary** PK populations.

The **primary PK population** will be defined as all subjects who receive the full dose of BPL HRIG / comparator HRIG and the first 3 doses of active rabies vaccine on Visits 2, 3, and 5, and for whom the PK sample at Visit 6 is taken. This population will be used for the primary PK analysis and selected secondary PK analyses. The **secondary PK population** will be defined as all subjects who receive the full dose of BPL HRIG / comparator HRIG and all 5 doses of active rabies vaccine and for whom all required PK samples are taken. This population will be used for selected secondary PK analysis and the exploratory analysis.

Subjects with a pre-dose RVNA of \geq the LLOQ will be excluded from the all

analyses.

[REDACTED]

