10.5.1. Primary PK Analysis

The primary efficacy analysis will be based on the primary PK population.

The primary hypothesis is that the proportion of subjects receiving BPL HRIG + active vaccine with an anti-rabies titer of ≥ 0.5 IU/mL will not be less than the corresponding proportion for subjects receiving comparator HRIG + active vaccine, by more than 0.1 at Visit 6. The Farrington and Manning test statistic will be used to assess the statistical comparison at a one-sided significance level of 0.025. It will be concluded that the BPL HRIG is non-inferior to the comparator HRIG if the lower limit of an exact binomial 95% confidence interval calculated from the Farrington-Manning score test is greater than the *a priori* set -10% non-inferiority margin.

An additional analysis will be performed to assess the impact of dosing/PK sampling not being performed on the designated day. See Section 10.7.2.

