The second secondary analyses will be performed using an appropriate mixed model repeated measures [MMRM] analysis to assess for differences of the slope and the change in GMT of the titers at the days described below. The correlation structure involves multiple pieces, including measurement errors, random variation, and inter-individual variability. For the longitudinal data analysis, an unstructured correlation matrix for within-subject error will be assumed. Other correlation structures, including compound symmetry, will be examined as needed. The validity of this model will be assessed via standard modeling diagnostics and goodness-of-fit measures. Comparisons of geometric mean titers [GMTs] between the treatment group at each timepoint and across all timepoints will be reported. The final output will include one row indicating the mean change [95% confidence intervals] in titer across all PK assessments from Visit 2 [baseline] through Visit 7 by treatment group and one row for every specific timepoint thereafter. Additionally, the difference in the means [or the ratio of the GMT] between treatment groups, the corresponding 95% confidence intervals, associated chi-square test statistic, and p-value will be reported. A p-value of <0.05 will signal a statistically significant difference in titers. See table below for example output:

Parameter	Treatment Group Ns			Mean Change From Baseline (95% Confidence Intervals)		BPL HRIG + Vaccine versus Comparator HRIG + Vaccine		
	N _{BPL}	N _{CP}	N _T	BPL HRIG + Vaccine	Comparator HRIG + Vaccine	Difference in Means (95% CI)	Chi-Square	P-Value
Through Day 28	x	x	x	x.xx (x.xx, x.xx)	x.xx (x.xx, x.xx)	x.xx (x.xx, x.xx)	x.xx	0.xxx
Day 3	x	x	x	x.xx (x.xx, x.xx)	x.xx (x.xx, x.xx)	x.xx (x.xx, x.xx)	x.xx	0.xxx
Day 5	x	x	x	x.xx (x.xx, x.xx)	x.xx (x.xx, x.xx)	x.xx (x.xx, x.xx)	x.xx	0.xxx
Day 7	x	x	x	x.xx (x.xx, x.xx)	x.xx (x.xx, x.xx)	x.xx (x.xx, x.xx)	x.xx	0.xxx
Day 14	x	x	x	x.xx (x.xx, x.xx)	x.xx (x.xx, x.xx)	x.xx (x.xx, x.xx)	x.xx	0.xxx
Day 28	x	x	x	x.xx (x.xx, x.xx)	x.xx (x.xx, x.xx)	x.xx (x.xx, x.xx)	x.xx	0.xxx

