1. a one-sided t-test will be used to assess non-inferiority of the mean of the AUC_{0-7d} of the BPL HRIG + vaccine group to the comparator HRIG + vaccine group. The pre-specified non-inferiority margin is 20%. It will be concluded the mean AUC_{0-7d} in the BPL HRIG + vaccine group is non-inferior to that in the comparator group if the lower limit of the 95% confidence interval for the mean AUC_{0-7d} is greater than -20% of comparator mean AUC_{0-7d}. Log-transformation of the AUC_{0-7d} data will be performed as necessary during statistical testing to meet assumptions for normality.

The null hypothesis is $(\mu_T - \mu_C) / \mu_T \leq -0.2$;

The alternative hypothesis is $(\mu_T - \mu_C) / \mu_T > -0.2$;

Where μ_T =the geometric mean of the AUC_{0-7d} in the BPL HRIG + vaccine group,

μ_C =the geometric mean of the AUC_{0-7d} in the comparator HRIG + vaccine group.

2. The geometric mean titers (GMTs) for RVNA titer up to peak serum level after administration of BPL HRIG and vaccine versus comparator HRIG and vaccine. Due to the observed change in relationship between time and titer level, only PK timepoints up to peak serum level will be included in this analysis.

A generalized estimating equation [GEE] for a repeated measures analysis will be used to assess the difference in proportions between the treatment groups for the third and fourth secondary efficacy analyses. Standard model building methods, diagnostics, and goodness-of-fit measures will be performed as appropriate. Proportions of subjects reaching set anti-rabies antibody titer will be compared at each timepoint as well as throughout all timepoints.

3. The proportion of subjects reaching anti-rabies antibody titer of ≥ 0.5 IU/mL at Visits 3-6 after administration of BPL HRIG and vaccine versus comparator HRIG and vaccine.
4. The proportion of subjects reaching anti-rabies antibody titer of \geq the lower limit of quantitation of the assay at Visit 3-6 after administration of BPL HRIG and vaccine versus comparator HRIG and vaccine. This titer threshold corresponds to the lower limit of quantitation of the assay.

The GEE analysis will include timepoints through Visit 6 for endpoints 3 and 4, at which point all or nearly all subjects are expected to have reached the stated thresholds. There is no clinical benefit of including subsequent timepoints in this analysis.

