5. The geometric mean titers (GMTs) for anti-rabies antibody titer at Visit 6-9 will be compared between treatment groups. Descriptive statistics and visual inspections will be reported as appropriate. No formal hypotheses testing will be performed.

g. EXPLORATORY PK ANALYSES

The following PK parameters for anti-rabies antibody concentrations will be summarized for both treatment groups:

- C_{\max} [IU/mL]
- T_{\max} [day]
- area under the concentration vs time curve to the last measurable concentration (AUC_{0-t}) [day*IU/mL]
- apparent terminal rate constant (λ_z) [day⁻¹]
- AUC_{0-7d} [day*IU/mL]
- area under the concentration vs time curve to infinity ($AUC_{0-\infty}$), if appropriate

- $C_{\max}/AUC_{0-\infty}$ [or C_{\max}/AUC_{0-t} if $AUC_{0-\infty}$ cannot be estimated]
- half-life ($t_{1/2}$), if appropriate

Non-compartmental PK methods will be utilized to calculate the subject level PK parameters. C_{\max} , AUC_{0-t} , AUC_{0-7d} , $AUC_{0-\infty}$, apparent terminal rate constant (λ_z), and $t_{1/2}$ will be dose normalized by dividing the raw PK parameters by the actual dose the subject received. A t-test will compare the PK and dose-normalized PK parameters between treatment groups. Log-transformations will be performed as necessary during statistical analysis when appropriate.

h. ADVERSE EVENT REPORTING

Adverse events (AEs) will be reported by the MedDRA system organ class and preferred term. Only treatment emergent AEs (i.e. beginning after dosing with BPL HRIG / vaccine or comparator HRIG / vaccine) will be included in the summary tables. All AEs will be included in the data listings.

Treatment-related AEs will be defined as events recorded as having a possible, probable or very likely/certain causality to treatment. AEs leading to withdrawal will be defined as events where the subject's participation in the study was discontinued as a result of the AE.

AEs will be summarized descriptively for all subjects and by treatment group. The denominator used for the calculation of percentages will be the number of subjects in the safety population per treatment group. For all AE summaries described below, counting will be performed by subject and event. For counts by subject, subjects experiencing the same event more than once will have that event counted only once within each system organ class and once within each preferred term.

The following summaries of treatment-emergent AEs will be provided:

SUMMARY OF AEs

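### Secondary endpoints 2–4 carry up to 16 unadjusted difference tests that the SAP counts as significant at two-sided 0.05, with no order, gate, adjustment or nominal label

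*SAP*

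**What the plan says.** The primary analysis is one comparison with its own level. Protocol 10.5.1 says: "The Farrington and Manning test statistic will be used to assess the statistical comparison at a one-sided significance level of 0.025".

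For the secondary endpoints, SAP 7.a gives one general rule: "The secondary efficacy endpoint analyses will be considered statistically significant using a two-sided significance level of 0.05". SAP 8.f then describes five analyses:

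- **Endpoint 1 (AUC0-7d):** a one-sided t-test of non-inferiority with a 20% margin, judged by the lower limit of a 95% confidence interval.
- **Endpoint 2 (geometric mean titers, mixed model):** "Comparisons of geometric mean titers [GMTs] between the treatment group at each timepoint and across all timepoints will be reported". The example table has a p-value in each of six rows: through Day 28, and Days 3, 5, 7, 14 and 28. The decision rule is: "A p-value of <0.05 will signal a statistically significant difference in titers". The numbered text below the table restricts the analysis to timepoints up to the peak titer.
- **Endpoints 3 and 4 (proportions at or above 0.5 IU/mL and at or above the LLOQ, GEE):** "Proportions of subjects reaching set anti-rabies antibody titer will be compared at each timepoint as well as throughout all timepoints". On the visits covered: "The GEE analysis will include timepoints through Visit 6 for endpoints 3 and 4".
- **Endpoint 5 (geometric mean titers, Visits 6–9):** "No formal hypotheses testing will be performed".

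Endpoints 2 and 5 use the secondary PK population; endpoints 1, 3 and 4 use the primary PK population. Only the PK parameter list in SAP 6 is labelled exploratory.

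**The concern.** The 7.a sentence is a decision rule, and 8.f applies it to many correlated comparisons of the same titers. Without an order, a gate, an adjustment or a label, a chance result below 0.05 at one visit would have the same stated standing as any other secondary finding. The trial is meant to support a US license application. A difference declared at an early visit bears on passive protection, and one declared at Day 14 or Day 28 bears on Objective 3 (interference with the vaccine response). The plan does not say in advance how much weight either would carry.

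Some contrasts also have two statuses at once, which is a problem whatever the error rate. And nothing makes the AUC0-7d non-inferiority conclusion depend on the primary being met.

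**Working it through.** **1. The plan's own figure.** The documents give no family-wise error rate for the secondaries. The one figure that can be reproduced is the primary sample size in protocol 10.9: 73 per group, from 98% success in both arms, margin 0.10, one-sided 0.025 and 85% power. With the Farrington–Manning variance under the null (restricted estimates 0.8895 and 0.9895):

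n = [1.960·√(0.8895·0.1105 + 0.9895·0.0105) + 1.036·√(2·0.98·0.02)]² / 0.10² = 72.4, so 73 per group.

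The figure reproduces. The primary is a single test at its own level, and nothing below changes its error rate.

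**2. Counting the difference tests in SAP 8.f.**

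| Endpoint | Test | p-values for a difference |
|---|---|---|
| 1 | One-sided non-inferiority | 0 |
| 2 | Mixed model: 5 days + overall | 6 (fewer if the peak restriction drops a visit) |
| 3 | GEE: Visits 3–6 + overall | 5 |
| 4 | GEE: Visits 3–6 + overall | 5 |
| 5 | Descriptive | 0 |
| Total | | up to 16 |

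Endpoint 1 is left out because equal products make its null hypothesis false; passing it would then be a correct conclusion.

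**3. Chance of at least one p < 0.05 with identical products.** Under independence this is 1 − 0.95^k: k = 16 gives 56.0%, k = 6 gives 26.5%, k = 3 gives 14.3%. For correlated tests I assumed normal statistics with a common pairwise correlation and simulated, rejecting if any |z| > 1.96:

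| Assumed correlation | 16 tests | 6 titer rows only | 3 overall tests only |
|---|---|---|---|
| 0 | 56% | 27% | 14% |
| 0.3 | 48% | 24% | 14% |
| 0.5 | 37% | 21% | 12% |
| 0.7 | 26% | 16% | 11% |
| 0.8 | 21% | 14% | 10% |
| 0.9 | 15% | 11% | 8% |

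As a second check, two identical arms of 73 were simulated with correlated log-titers. The titer levels and within-subject correlations (0.3–0.9) were assumed, and simple t-tests and proportion tests stood in for the mixed model and GEE. At least one p < 0.05 occurred in about 20% to 42% of trials over all tests, about 10% to 22% for the titer rows alone, and 7% to 14% for the three overall tests alone. The lower part of the all-tests range (about 20–31%) arises when nearly everyone exceeds the LLOQ early, so that endpoint 4 adds almost nothing.

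**4. Status conflicts, which need no simulation.**

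- Day 14 and Day 28 geometric mean titers are Visits 6 and 7. Under endpoint 2 they are tested at 0.05; under endpoint 5, in the same population, they have no formal test.
- The Day 14 proportion at or above 0.5 IU/mL is the primary non-inferiority endpoint. Under endpoint 3 it is compared again for a difference, also in the primary PK population.
- AUC0-7d is secondary endpoint 1 with a non-inferiority margin, and also an exploratory parameter compared by t-test (SAP 6 and 8.g).
- The two-sided 0.05 sentence in 7.a fits neither endpoint 1 (one-sided) nor endpoint 5 (untested).

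**The case against.** The best defense has four parts.

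- **The primary is untouched.** It is one test at one-sided 0.025 with no interim analysis. A reader might infer that the trial's main conclusion has an inflated error rate; the documents do not support that. Nor do they propose a labeling claim from the secondaries, or say that AUC0-7d would be claimed after a failed primary. They only fail to rule it out.
- **Not every secondary is affected.** A reader might take 7.a to mean that all five endpoints are tested for a difference. The specific text in 8.f overrides that for endpoints 1 and 5. Only endpoints 2–4 can give a spurious difference.
- **Sixteen is an upper count.** The six rows come from an example table, and the peak restriction may remove a visit. The explicit p-value sentence belongs to endpoint 2; for endpoints 3 and 4 the level comes from 7.a, and the four-visits-plus-overall count is inferred from the instruction to compare at each and across all timepoints. Near the ceiling a test also falls below its nominal size: at the planned 98% with 73 per arm, a two-sided score test for a difference at Day 14 rejects about 2.7% of the time, and at 99% about 0.6%.
- **The size rests on unseen inputs.** A single figure such as one trial in three cannot be derived, because the documents give no correlations or titer variances.

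All four stand, and they limit the point to what is claimed here. They do not remove it: the titer rows alone, which carry the explicit rule, give at least about twice 5% in the runs made, and the status conflicts remain. Redaction is an unlikely explanation for the missing rule, since protocol 10.5.3 and 10.9 are not blacked out and contain no order or adjustment. Protocol 10.9 mentions an overall study alpha of 0.05 but does not tie the secondaries to it.

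**Conclusion.** The point holds for secondary endpoints 2–4. The SAP treats unadjusted p < 0.05 as statistical significance across up to 16 difference tests, and neither document orders, gates, adjusts or labels them. With identical products, the chance of at least one declared difference is about 20–40% under plausible assumed correlations, with 15% (correlation 0.9) and 56% (independence) as the outer values. It is about 10–22% for the titer rows alone, and 14% or less if only the three overall tests were counted, a limit the SAP does not set. These figures depend on assumed correlations and titer levels; the absence of control and the conflicting status of the Day 14 and Day 28 titers do not. This is a labeling and error-control defect in the secondary analyses, worth correcting because correction is cheap. It is not a threat to the primary conclusion.

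**What to change.** Before unblinding:

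1. In SAP 7.a, replace the secondary sentence. Limit confirmatory testing to the primary at one-sided 0.025 and then, only if it is met, AUC0-7d non-inferiority at one-sided 0.025 (lower limit of the two-sided 95% interval). Labeling all secondaries supportive would also be acceptable; gating AUC0-7d is one reasonable choice, not the only one.
2. In SAP 8.f, report endpoints 2–4 as estimates with 95% confidence intervals and nominal p-values, and delete the sentence "A p-value of <0.05 will signal a statistically significant difference in titers".
3. Give the Day 14 and Day 28 geometric mean titers the same non-confirmatory status under endpoints 2 and 5.
4. In SAP 8.f and protocol 10.5.3, state that the Day 14 row of endpoint 3 neither replaces nor qualifies the primary analysis.

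The cost is a few sentences, with no new data, subjects or analyses. The downside is that endpoints 2–4 can no longer be called statistically significant, and AUC0-7d non-inferiority cannot be claimed if the primary fails.
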